5.5 Withdrawal Criteria (if applicable)

If at any time during the study the investigator determines that a subject's safety has been compromised, the subject may be withdrawn from the study.

Subjects may withdraw consent from the study at any time.

Sponsor and/or investigator may discontinue any subject for non-compliance or any valid medical reason (see Section 8.6.2).

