- Fluorescein staining – [REDACTED] Scale;
- [REDACTED] [REDACTED] Scale;
- [REDACTED]
- [REDACTED]
- Dispensation of study drug kit according to randomization for [REDACTED] until Visit 5;
- [REDACTED]
- [REDACTED]
- [REDACTED]

- [REDACTED]
 - [REDACTED]
 - [REDACTED]
 - [REDACTED]
- Adverse event query;
- Schedule subjects for Visit 5.

[REDACTED]

■ [REDACTED]

Visit 5 (Day 57 ± 4): 8-Week CAE[®] Test/ End of Double-Masked Treatment

- Collection and review of study drug and subject diaries;
- Medical / medication history update;
- Adverse event query;
- Urine pregnancy test (for females of childbearing potential);
- [REDACTED] Ocular Discomfort Scale;
- [REDACTED] Ocular Discomfort Scale & 4-Symptom Questionnaire;
- [REDACTED]
- Visual acuity;
- Slit-lamp biomicroscopy;
- [REDACTED] [REDACTED]
- [REDACTED]
- TFBUT;
- Fluorescein staining [REDACTED]
- Lissamine Green staining [REDACTED]
- [REDACTED]
- [REDACTED]
- [REDACTED]
- [REDACTED]
 - [REDACTED]

- [REDACTED] Ocular Discomfort Scale;
- [REDACTED] Ocular Discomfort Scale & 4-Symptom Questionnaire;
- Slit-lamp biomicroscopy;
- [REDACTED] [REDACTED]
- [REDACTED]
- TFBUT;
- Fluorescein staining [REDACTED]
- [REDACTED] [REDACTED]
- Intraocular pressure;
- Dilated funduscopy;
- Adverse event query;
- Study Exit.

Early Termination/Discontinuation

If a subject is discontinued from the study prior to Visit 5 (Day 57 ± 4), then all safety evaluations and [REDACTED] [REDACTED] that are to be performed at Visit 5 should be performed on the day of discontinuation (early termination) or at the discretion of the investigator.

Adverse Events (both elicited and observed) and SAEs will be monitored throughout the study. The investigator will promptly review all adverse events (both elicited and observed) for accuracy and completeness. All adverse events will be documented on the appropriate source document and eCRF.

If a female reports a pregnancy or has a positive pregnancy test during the study, then the investigator will notify Ora immediately. The investigator shall instruct the patient to immediately stop the study medication and request from the subject and/or the subject's physician copies of all related medical reports during the pregnancy and shall document the outcome of the pregnancy. The investigator will retain these reports together with the subject's source documents and will provide a copy of all documentation to Ora.

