8.4 Schedule of Visits, Measurements and Dosing

8.4.1 Scheduled Visits

Refer to Appendix 1 for a schedule of visits and measurements.

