8.4.2 Unscheduled Visits

These visits may be performed in order to ensure subject safety. All procedures performed at an unscheduled visit will be recorded in the source documents and on the Unscheduled Visit eCRF pages. Any procedure indicated in the eCRF that is not performed should be indicated as “Not done.”

Evaluations that may be conducted at an Unscheduled Visit include:

- Slit-lamp Biomicroscopy;
- Visual Acuity;
- Intraocular Pressure;
- Pregnancy Test;
- Dilated Fundoscopy;
- Assessment of Adverse Events;
- Assessment of concomitant medications and/or treatments; and
- Any other assessments needed in the judgment of the investigator.

8.5 **Compliance with Protocol**

Subjects will be instructed on proper [REDACTED] instillation and storage of study drug at the end of Visits 1, 2, 3, and 4 and given written instructions.

[REDACTED]

[REDACTED] These guidelines will be used by the Investigator for determining the subject’s necessary compliance for the study and for recording deviations from this compliance.

8.6 **Subject Disposition**

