8.6.2 Discontinued Subjects

Subjects may be discontinued prior to their completion of the study due to:

- adverse events;
- protocol violations;

- administrative reasons (e.g., inability to continue due to scheduling changes);
- lost to follow up;
- sponsor termination of study;
- subject choice (e.g. withdrawal of consent); and
- other

Note: In addition, any subject may be discontinued for any sound medical reason at the discretion of the investigator.

Notification of a subject discontinuation and the reason for discontinuation will be made to Ora and/or study sponsor and will be clearly documented on the eCRF.

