10 STATISTICAL HYPOTHESES AND METHODS OF ANALYSES

10.1 Analysis Populations

Intent-to-Treat Population – The intent-to-treat (ITT) population includes all randomized subjects. The primary and secondary efficacy analyses will be performed on the ITT population. Subjects in the ITT population will be analyzed as randomized.

Per-Protocol Population – The per protocol (PP) population excludes subjects with significant protocol deviations or who do not complete the study. Protocol deviations will be assessed and the per protocol population identified prior to database lock and unmasking. Subjects in the PP population will be analyzed as treated.

Safety Population – The safety population will include all subjects receiving treatment from whom at least one safety measurement is obtained following the first dose of study drug. The safety population will be analyzed for all safety assessments. Subjects in the Safety population will be analyzed as treated.

In addition, the following populations are defined for the primary and key secondary analyses of conjunctival fluorescein staining:

ITTCFS Population – The ITTCFS population includes all subjects in the ITT population with [REDACTED]

PPCFS Population – The PPCFS population includes all subjects in the PP population with [REDACTED]

The statistical analysis of safety data will be performed for the safety population. The primary efficacy analysis of Ocular Discomfort will be performed on the ITT population. The primary efficacy analysis of conjunctival fluorescein staining will be performed on

the ITTCFS population. Key secondary efficacy analyses will be performed on the ITT population, except for analysis of conjunctival fluorescein staining, which will be performed on the ITTCFS population. Exploratory efficacy analyses will be performed on the ITT population. The primary efficacy analysis procedures will also be performed on the PP and PPCFS populations as sensitivity analyses, for Ocular Discomfort and conjunctival fluorescein staining, respectively.

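### Sections 5.5 and 8.6.2 allow follow-up to end for non-compliance or protocol violations, a probably small but avoidable source of missing ITT data; the key secondaries have no imputation-based check

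*Combined protocol and SAP*

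**What the plan says.** **Removal.** Section 5.5 states: "Sponsor and/or investigator may discontinue any subject for non-compliance or any valid medical reason (see Section 8.6.2"). The wording is permissive. Section 8.6.2 opens with "Subjects may be discontinued prior to their completion of the study due to" and its list includes "protocol violations". What ends is study participation, not only study drug. Section 8.6.1 defines a completed subject as anyone not discontinued from the study, so no status is visible for a subject who has deviated but is still followed.

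**Follow-up after removal.** Section 8.3.1 covers early termination: "If a subject is discontinued from the study prior to Visit 5", all safety evaluations and some redacted items "that are to be performed at Visit 5 should be performed on the day of discontinuation (early termination) or at the discretion of the investigator". For the visit schedule, Section 8.4.1 says only "Refer to Appendix 1 for a schedule of visits and measurements", and that appendix is not in the public text.

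**Handling of deviations.** Section 8.5 has partly redacted guidelines that the investigator uses to judge "necessary compliance for the study and for recording deviations from this compliance". Section 10.1 says "The intent-to-treat (ITT) population includes all randomized subjects", analysed as randomised. PP, and PPCFS within it, leave out significant deviators and non-completers.

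**Missing data.** Section 10.4.3 plans MCMC multiple imputation for missing Day 57 primary data, with control-based pattern mixture, LOCF and observed-data sensitivity analyses. Sections 10.4.3 and 10.4.6 rule out imputation for the key secondaries. Their listed sensitivity analyses are t-tests, Wilcoxon tests, and PP or PPCFS observed data. Section 10.4.4 puts all four in the hierarchy that controls study-wide type I error at 0.05.

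**The concern.** ITT is meant to keep every randomised subject in the comparison. Removing someone for behaviour after randomisation keeps the name in the set but loses the outcome, and here the loss follows from a sponsor or investigator decision. That distinguishes it from withdrawn consent or loss to follow-up, which the protocol can influence much less. The removal also gains nothing analytically: the deviation is recorded in any case, and PP drops a significant deviator whether or not the subject stays in follow-up.

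At stake is how far the primary results rest on imputed values, and how far the key secondary results rest on whoever happens to be observed. For the key secondaries, no planned analysis replaces missing values under a different assumption, yet each can support a confirmatory claim.

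**Working it through.** **1. Which endpoints a removal can cost.** Both primaries are at Visit 5. From Section 6.1.2, two key secondaries are at Visit 3 (Ocular Discomfort, central corneal staining), one at Visit 4 (conjunctival staining) and one at Visit 5 (TFBUT pre- to post-CAE).

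| Removed | Primaries at risk | Key secondaries at risk |
|---|---|---|
| Before Visit 3 | 2 | 4 |
| Between Visits 3 and 4 | 2 | 2 |
| After Visit 4 | 2 | 1 |

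An early-termination assessment could count as Day 57 data only if the redacted items include the efficacy measure and the assessment falls within Day 57 ± 4. Returning at Visit 5 alone would recover both primaries but only one of the four key secondaries.

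**2. Effect size for scale.** The effect, SD and attrition assumptions are redacted, so 284 per group cannot be reproduced from the plan's own inputs. Solving backwards (noncentral t, two-sided 0.05, 284 per group, 90% power) gives d = 0.2725 SD. The normal approximation gives (1.960 + 1.282) × √(2/284) = 0.272. This is an assumption, and it returns 284 by construction. Power at 300 per arm is 91.5%. The unadjusted standard error is √(2/300) = 0.0816 SD.

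**3. Possible overstatement.** Let q be the share of each arm removed for these two reasons (assumed 1%, 2.5% or 5%, that is 3, 7.5 or 15 of 300) and r the share of benefit kept after non-compliance. If the imputation in effect assigns full benefit, and the target counts outcomes after non-compliance, then overstatement = d × q × (1 − r).

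| q | r = 0 | % of SE | r = 0.5 | % of SE |
|---|---|---|---|---|
| 1% | 0.0027 SD | 3.3% | 0.0014 SD | 1.7% |
| 2.5% | 0.0068 SD | 8.3% | 0.0034 SD | 4.2% |
| 5% | 0.0136 SD | 16.7% | 0.0068 SD | 8.3% |

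With r = 1 the overstatement is zero. For d from 0.20 to 0.35, the q = 5%, r = 0 case runs from 0.05 × 0.20 = 0.010 to 0.05 × 0.35 = 0.0175 SD. These figures describe an endpoint analysed in all 300 per arm. The size of the ITTCFS subset is redacted.

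**4. How plausible the range is.** Planned enrolment exceeds the stated requirement by 300 − 284 = 16 per arm, and 16/300 = 5.3%. If that is the whole attrition allowance (an assumption, since the text is redacted), q = 5% would mean that nearly all attrition came from these two reasons. It is therefore a high value.

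**5. Power if these subjects are followed instead.** With them missing, n = 300(1 − q) per arm and the effect is d. With them followed, n = 300 and the effect is d(1 − q(1 − r)).

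| q | Missing | Followed, r = 0 | Followed, r = 0.5 | Followed, r = 1 |
|---|---|---|---|---|
| 1% | 91.2% | 91.0% | 91.2% | 91.5% |
| 2.5% | 90.8% | 90.1% | 90.8% | 91.5% |
| 5% | 90.1% | 88.6% | 90.1% | 91.5% |

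At q = 5% the change runs from −1.5 to +1.4 points. The case for follow-up is therefore not one of power.

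**The case against.** The strongest reply is that nothing here is an error. The two sections are permissive, agree with each other, and do not conflict with the ITT definition. That stands, and it is why the point is a design improvement.

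Second, much of the relevant text is hidden: Appendix 1, parts of 8.3.1 and 8.5, and the passages after the MCMC sentences in 10.4.3 and 10.4.5, where the imputation details would sit. The early-termination items beyond safety may well be efficacy measures. This also stands. The absence can be claimed only for visible text, and the overstatement formula assumes something about the imputation that cannot be checked. It does not rescue removals well before Visit 5, because a value taken on the day of discontinuation is not then a Day 57 value.

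Third, the design makes such removals less likely or less harmful. A 7-day placebo run-in is used for subject selection, exclusion u screens out people unwilling to follow instructions or attend all visits, and masking limits arm-dependent decisions. The documents give no support for any particular rate. In addition, a protocol violation need not involve missed drug, so the benefit may be fully kept, and some non-compliant subjects would not attend further visits anyway. All of this lowers the likely size without removing the gap.

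Fourth, a reader might infer that the key secondaries have no missing-data check at all. That goes too far. Section 10.4.3 itself counts observed-data analyses, including PP and PPCFS, among its missing-data methods for the primaries, and the key secondaries have analyses of that type. What they lack is any imputation-based check.

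**Conclusion.** The point holds as a low-severity improvement. On the visible text, the plan allows outcomes that consenting subjects could have given to go missing for reasons already handled by deviation recording and by PP/PPCFS. The number affected is unknown and could be near zero.

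The illustrative 0.003 to 0.014 SD (3% to 17% of one standard error) rests on four assumptions: 1% to 5% removed, d of about 0.272 SD, no retained benefit, and imputation that in effect assigns full benefit. It is an overstatement only if the intended target counts outcomes after non-compliance, and no estimand is visible.

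A reader might infer that the plan requires removal of non-compliant subjects, or that the primary result is materially biased. The documents support neither. The wording is permissive, and the primaries have MCMC imputation with several sensitivity analyses, including a control-based one. The gap for the key secondaries is separate and does not depend on the removal rate, because it concerns missing data from any cause.

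**What to change.** **Change 1, Sections 5.5 and 8.6.2.** State that non-compliance or a protocol violation is not in itself a reason to end follow-up. Ask subjects who have not withdrawn consent to attend all remaining scheduled visits (3, 4 and 5 as applicable), and use those values in ITT and ITTCFS. Continue to handle deviations through Section 8.5 and PP/PPCFS. Rules on study drug, withdrawal for safety and withdrawal of consent stay as they are. The cost is a protocol amendment, a site instruction, some effort to keep a small number of subjects attending (Visit 5 includes the CAE test), and the power change shown above.

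**Change 2, Section 10.4.6, separate from the first.** Add for each key secondary endpoint the control-based multiple imputation sensitivity analysis that Section 10.4.3 already plans for the primaries. The cost is one extra analysis per endpoint, four in all, with no new data and no use of alpha.

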6 STUDY PARAMETERS

6.1 Efficacy Measures

6.1.1 Primary Efficacy Measures

The primary endpoints will be tested in a hierarchical fixed sequence in the following order:

1. Change from baseline (Visit 2) in Ocular Discomfort at Visit 5 (Day 57) [REDACTED]
2. Change from baseline (Visit 2) in conjunctival fluorescein staining (sum of temporal and nasal regions) at Visit 5 (Day 57) [REDACTED]

6.1.2 Key Secondary Efficacy Measures

The key secondary efficacy endpoints will be tested in a hierarchical fixed sequence in the following order:

1. Change from baseline (Visit 2) in Ocular Discomfort at Visit 3 (Day 29) [REDACTED]
2. Change from baseline (Visit 2) in conjunctival fluorescein staining (sum of temporal and nasal regions) at Visit 4 (Day 43) [REDACTED]
3. Tear film break-up time pre- to post- CAE[®] at Visit 5 (Day 57) in the worst eye at baseline;
4. Change from baseline (Visit 2) in corneal fluorescein staining in central region at Visit 3 (Day 29) [REDACTED]

6.1.3 Criteria for Effectiveness

The primary efficacy variables will be evaluated to assess effectiveness. For this phase 3 study, the primary analyses will each be evaluated at two-sided alpha levels of 0.05 (SkQ1 ophthalmic solution versus placebo) to determine evidence of efficacy. Testing will follow a hierarchical testing strategy, where efficacy for each endpoint and comparison to placebo will be determined only if the preceding test(s) are statistically significant.

6.2 Safety Measures

- Visual acuity (ETDRS);

- Slit-lamp biomicroscopy;
- Adverse event query;
- Dilated funduscopy;
- Intraocular pressure.

7 STUDY MATERIALS

7.1 Study Drug(s)

7.1.1 Run-In

Placebo SkQ1 ophthalmic solution (Vehicle of SkQ1 ophthalmic solution)

7.1.2 Study Drug(s)/ Formulation(s)

- 1.55 µg/mL SkQ1 ophthalmic solution
- Placebo SkQ1 ophthalmic solution (Vehicle)

7.1.3 Study Drug Packaging Configuration

[REDACTED]

All study drug will be labeled according to applicable regulatory requirements.

7.1.4 Study Drug Storage and Accountability

The study drug must be stored in a secure area accessible only to the investigator and his/her designees. The study drug will be administered only to subjects entered into the clinical study, in accordance with the conditions specified in this protocol. [REDACTED]

[REDACTED]

The study drug is to only be prescribed by the principal investigator or his/her named sub investigator(s), and is to only be used in accordance with this protocol. The study drug must only be distributed to subjects properly qualified under this protocol to receive study drug. The investigator must keep an accurate accounting of the study drug by maintaining a detailed inventory. This includes the amount of study drug received by the site, amount dispensed to subjects, amount returned to the site by the subjects, and the amount returned to the Sponsor upon the completion of the study.

7.1.5 Instructions for Dispensation, Use, and Administration

At the end of Visit 1, qualified subjects will receive a kit [REDACTED]

At Visit 2, the run-in kit will be collected from subjects for drug accountability. At the end of Visit 2, qualified subjects will be randomized [REDACTED]

At Visit 3, the study drug kit will be collected from subjects for drug accountability. [REDACTED]

At Visit 4, the study drug kit will be collected from subjects for drug accountability. [REDACTED]

At Visits 5 the study drug kit will be collected from subjects for drug accountability.

[REDACTED]

If needed, replacement kits are also available to be dispensed to a subject.

7.2 **Other Study Supplies**

Ora to provide sites with urine pregnancy tests, Schirmer's test strips, sodium fluorescein, lissamine green, tear collection supplies.

8 **STUDY METHODS AND PROCEDURES**

8.1 **Subject Entry Procedures**

8.1.1 Overview

Subjects as defined by the criteria in Sections 5.2, 5.3, and 5.4 will be considered for entry into this study.

8.1.2 Informed Consent

Prior to a subject's participation in the trial (i.e., prior to changes in a subject's medical treatment and/or prior to study related procedures), the study will be discussed with each subject, and subjects wishing to

participate must give written informed consent using an informed consent form (ICF). The informed consent form must be the most recent version that has received approval/favorable review by a properly constituted Institutional Review Board (IRB).

8.1.3 Washout Intervals

Prohibited medications, treatments, and activities are outlined in the Exclusion Criteria (Section 5.4).

8.1.4 Procedures for Final Study Entry

Subjects must meet all inclusion and none of the exclusion criteria.

8.1.5 Methods for Assignment to Treatment Groups:

Prior to initiation of study run-in (at Visit 1), each subject who signs the informed consent will be assigned a screening number. All screening numbers will be assigned in strict numerical sequence at each site and no numbers will be skipped or omitted.

At Visit 2, a patient who meets all the eligibility criteria will be randomized to receive treatment with 1.55 µg/mL SkQ1 Ophthalmic Solution or placebo in a 1:1 ratio [REDACTED]

Subjects will be assigned to treatment groups using stratified random sampling and stratification [REDACTED]

[REDACTED]

[REDACTED] The site staff will dispense to the patient the study kit labeled with the corresponding kit number. Both the randomization number and the dispensed study drug kit number will be recorded on the patient's source document and eCRF. Kit numbers for returned bottles will also be recorded for each visit.

8.2 Concurrent Therapies

The use of any concurrent medication, prescription or over-the-counter, is to be recorded on the subject's source document and corresponding electronic case report form (eCRF) along with the reason the medication was taken.

Concurrent enrollment in another investigational drug or device study is not permitted.

8.2.1 Prohibited Medications/Treatments

Disallowed medications/treatments during the study are outlined in the Exclusion Criteria (Section 5.4).

8.2.2 Escape Medications

No escape medications are required for this study.

8.2.3 Special Diet or Activities

No special diets or activities are required for this study.

8.3 Examination Procedures

8.3.1 Procedures to be Performed at Each Study Visit with Regard to Study Objective(s)

The following procedures will be performed (see Appendix 2 for description):

Visit 1 (Day -7 -2/+1 days): Screening

- Informed consent / Health Information Portability and Accountability Act (HIPAA);
- Demographic data and medical / medication history;
- Urine pregnancy test (for females of childbearing potential);
- [REDACTED] Ocular Discomfort Scale;
- [REDACTED] Ocular Discomfort Scale & 4-Symptom Questionnaire;
- [REDACTED]
- Visual acuity;
- Review of qualification criteria;
- Slit-lamp biomicroscopy;
- [REDACTED] [REDACTED]
- [REDACTED]
- Tear Film Break-up Time (TFBUT);
- Fluorescein staining [REDACTED]

- [REDACTED];
- [REDACTED]
- [REDACTED]
- Intraocular pressure;
- Dilated funduscopy;
- Review of qualification criteria;
- Adverse event query;
- Dispensation of run-in (RUN-IN) for [REDACTED] until Visit 2;
 - [REDACTED]
- [REDACTED]
 - [REDACTED]
- Dispensation of diaries and subject instructions;
 - [REDACTED]
 - [REDACTED]
 - [REDACTED]
 - [REDACTED]
- Qualified subjects will be scheduled for Visit 2.

Visit 2 (Day 1): Baseline/Screening Confirmation/ Randomization and Initiation of Double-Masked Treatment

- Collection and review of run-in (RUN-IN) and subject diaries;
- [REDACTED]
- Medical/medication history update;
- Adverse event query;
- [REDACTED] Ocular Discomfort Scale;

- [REDACTED] Ocular Discomfort Scale & 4-Symptom Questionnaire;
- [REDACTED]
- Visual acuity;
- Slit-lamp biomicroscopy;
- [REDACTED]
- [REDACTED]
- TFBUT;
- Fluorescein staining [REDACTED]
- [REDACTED] [REDACTED]
- [REDACTED]
- [REDACTED]
- Review of qualification criteria;
- Randomization;
- Dispensation of study drug kit according to randomization for [REDACTED] until Visit 3;
- [REDACTED]
 - [REDACTED]
- [REDACTED]
- [REDACTED]
- [REDACTED]
 - [REDACTED]
 - [REDACTED]
 - [REDACTED]
- Adverse event query;
- Schedule subjects for Visit 3.

○ [REDACTED]

- Adverse event query;
- Schedule subjects for Visit 4.

[REDACTED]

■ [REDACTED]

Visit 4 (Day 43 ± 2 days): 4-Week Follow-up

- Collection and review of study drug and subject diaries;
- [REDACTED]
- Medical / medication history update;
- Adverse event query;
- [REDACTED] Ocular Discomfort Scale;
- [REDACTED] Ocular Discomfort Scale & 4-Symptom Questionnaire;
- [REDACTED]
- Visual acuity;
- Slit-lamp biomicroscopy;
- [REDACTED] [REDACTED]
- [REDACTED]
- TFBUT;
- Fluorescein staining – [REDACTED] Scale;
- [REDACTED] [REDACTED] Scale;
- [REDACTED]
- [REDACTED]
- Dispensation of study drug kit according to randomization for [REDACTED] until Visit 5;
- [REDACTED]
- [REDACTED]
- [REDACTED]

- [REDACTED]
 - [REDACTED]
 - [REDACTED]
 - [REDACTED]
- Adverse event query;
- Schedule subjects for Visit 5.

[REDACTED]

■ [REDACTED]

Visit 5 (Day 57 ± 4): 8-Week CAE[®] Test/ End of Double-Masked Treatment

- Collection and review of study drug and subject diaries;
- Medical / medication history update;
- Adverse event query;
- Urine pregnancy test (for females of childbearing potential);
- [REDACTED] Ocular Discomfort Scale;
- [REDACTED] Ocular Discomfort Scale & 4-Symptom Questionnaire;
- [REDACTED]
- Visual acuity;
- Slit-lamp biomicroscopy;
- [REDACTED] [REDACTED]
- [REDACTED]
- TFBUT;
- Fluorescein staining [REDACTED]
- Lissamine Green staining [REDACTED]
- [REDACTED]
- [REDACTED]
- [REDACTED]
- [REDACTED]
 - [REDACTED]

- [REDACTED] Ocular Discomfort Scale;
- [REDACTED] Ocular Discomfort Scale & 4-Symptom Questionnaire;
- Slit-lamp biomicroscopy;
- [REDACTED] [REDACTED]
- [REDACTED]
- TFBUT;
- Fluorescein staining [REDACTED]
- [REDACTED] [REDACTED]
- Intraocular pressure;
- Dilated funduscopy;
- Adverse event query;
- Study Exit.

Early Termination/Discontinuation

If a subject is discontinued from the study prior to Visit 5 (Day 57 ± 4), then all safety evaluations and [REDACTED] [REDACTED] that are to be performed at Visit 5 should be performed on the day of discontinuation (early termination) or at the discretion of the investigator.

Adverse Events (both elicited and observed) and SAEs will be monitored throughout the study. The investigator will promptly review all adverse events (both elicited and observed) for accuracy and completeness. All adverse events will be documented on the appropriate source document and eCRF.

If a female reports a pregnancy or has a positive pregnancy test during the study, then the investigator will notify Ora immediately. The investigator shall instruct the patient to immediately stop the study medication and request from the subject and/or the subject's physician copies of all related medical reports during the pregnancy and shall document the outcome of the pregnancy. The investigator will retain these reports together with the subject's source documents and will provide a copy of all documentation to Ora.

